3.2.2.1 Adverse events

Adverse events will be coded using the Medical Dictionary for Regulatory Activities (MedDRA) Version 22.0.

Listings will be presented and sorted by treatment group, subject id, start time of AEs, primary system organ class, preferred term and verbatim text for all adverse events recorded during the study.

Listings of serious adverse events (SAE), adverse events leading to withdrawal and listings of deaths will also be presented.

Adverse events will be monitored from the time that the subject gives informed consent and throughout the study until 7 days after the end of study treatment. A TEAE is defined as any AE that occurs during the active phase of the study (i.e. from the first study drug intake until 48h after last study drug intake) and if:

- it was not present prior to receiving the first dose of IMP, or
- it was present prior to receiving the first dose of IMP but the intensity increased during the active phase of the study, or
- it was present prior to receiving the first dose of IMP, the intensity is the same but the drug relationship became related during the active phase of the study.

Treatment Emergent Adverse Events (TEAE) will be flagged (*) in the adverse events listing and will be summarised.

Related adverse events are those events with causality missing or related.

An overall summary table of all AEs with the number and percentage of subjects with at least one:

- AE,
- TEAE,
- TEAE by intensity,
- TEAE by causality,
- TEAE by intensity and causality,
- SAE,
- TEAE leading to premature withdrawal of study.

Note: In the event of multiple adverse events (corresponding to different PTs) being reported by the same subject, each subject is counted for each intensity level, each causality level or each intensity and causality combined level. That means that the total of subjects for all levels of intensity / causality might be higher than the overall number of subjects with at least one AE.

Incidence of all reported AEs, TEAEs, SAEs and non-serious AES (classified by primary System Organ Class (SOC) and Preferred Term (PT)) will be tabulated by treatment group. In addition, summary tables will be presented by maximum intensity, drug relationship and TEAEs/SAEs associated with premature withdrawal of study.

Note: In the event of multiple occurrence of a same AE (same Preferred Term) by the same subject, the maximum intensity (severe > missing > moderate > mild) and the most serious causality (related > not related) will be chosen.

SAP Final Version: 15 July 2019

27/50

Note: In case of missing data for relationship/intensity, the AE (PT) will be presented with the most severe category (related and/or severe) when crossing intensity and relationship.

3.2.2.2 *Laboratory data*

Not applicable.

3.2.2.3 *Vital signs*

Vital signs will be listed at each assessment by treatment group and subject. Any unscheduled vital signs will be flagged [U] in the listing.

Baseline values (values at first visit) will be defined as the last vital signs measurement collected prior to the first dose of study drug.

Summary statistics by treatment group will be presented (blood pressure, heart rate in sitting position, body temperature and body weight) at each scheduled assessment for actual values and changes from baseline.

3.2.2.4 *ECG*

Not applicable.

3.2.2.5 *Other assessments (as applicable)*

Any new or worsening clinically significant abnormal physical examination results should be recorded on the Adverse Event eCRF page and will be part of the AE analysis.

3.2.3 *Missing data and outliers*

3.2.3.1 *Missing data*

If there is a significant number of missing values for a subject (or if there is confirmed data appearing spurious), a decision will be made following consultation with the sponsor regarding the handling of these data in summaries, prior to breaking the blind.

Any repeat or additional assessments performed will be included in the individual subject data listings.

3.2.3.2 *Missing or incomplete dates*

Missing date and/or time related to stools in patients diaries for time-to-event analyses (time to recovery, time to first formed stool, time to last watery stool, time to recovery without confirmation):

Rules of imputation for events: in case of time information is missing but information on date and on stool consistency are available, the time will be imputed:

- to 23:59 if there is no other subsequent stools the same day,
- to time of the next stool the same day minus 1 minute otherwise.

Rules of imputation for censoring: in case of time information is missing but information on date and on stool consistency are available, the time will be imputed:

- to the half of the interval (i.e. to $(24:00 - \text{time of last stool}) / 2$) if there is at least one non-missing time the last day
- to 12:00 a.m. if there is no other available times the last day

Missing first administration time for time-to-event analyses:

If time of first administration is missing for a subject, it will be imputed with the date/time of the first stool after randomization as recorded in the diary. If date/time of randomization is also missing, time of first intake will be imputed with the time of the first stool of the diary.

Other:

In all listings, missing or incomplete dates should be left as they have been recorded. However, for calculation / sorting / assignation based on dates, the following methods will be used:

- (1) The most conservative approach will be systematically considered (i.e. if the onset date of an AE/concomitant medication is missing / incomplete, it is assumed to have occurred during the study treatment phase (i.e. a TEAE for AEs) except if the partial onset date or other data [stop date, ...] indicates differently).
- (2) A missing/incomplete date of medical history or disease diagnosis will be assumed to have occurred before any study treatment.
- (3) If a partial date and the associated information do not allow to state about the assignation to a group / category, all the possible groups / categories will be considered (i.e.: an AE could be assigned to several possible doses at event onset according to its partial onset date and stop date. Particularly an AE with missing start date will be assigned to each dose received before its end date. Similarly a medication with partial start and stop dates could be considered as prior and concomitant treatment).
- (4) Where this is possible, the derivations based on a partial date will be presented as superior inequalities (i.e.: for an AE started in FEB2004 after the administration performed on 31JAN2004, the days since last dose will be " ≥ 2 ", similarly the duration of ongoing AEs or medication will be " $\geq xx$ " according to the start and last visit dates).

3.2.3.3 *Outliers*

Any outlier identified prior to unblinding which is impossible/unplausible will be excluded from the analysis. For other identified outliers, the impact should be assessed by performing the statistical analysis with the actual values and at least one other analysis eliminating or reducing the outlier effect.

If any outliers are identified after unblinding the statistical analysis should be performed with the actual values and at least one other analysis eliminating or reducing the outlier effect.

A search of outliers/missing values by BIOTRIAL should be performed before the unblinding and actions with the sponsor should be defined. This will be done for variables used for the primary and secondary analysis. A specific focus will be on the DEB data and especially on the dates and times of each recorded stool (missing values and chronological order) and their consistencies including summaries of number of stools overall and according to Bristol scale). The date/time of first watery stool (i.e. diarrhoea onset) recorded on the eCRF will also be examined (if time missing) as well as the number of stools and watery stools during the last 24

hours period (baseline data). A detection of abnormal values for raw and changes from baseline on vital signs data will also be performed.

3.2.4 *Subject disposition*

A listing of dates of assessments (relative day) and their study exposure will be presented by subject for each treatment group. A summary table will present the extent of subject exposure in the study for each treatment group.

The numbers and percentages of subjects in each of the ITT, mITT, PP and safety populations will be tabulated by country. The reasons for subject exclusions from each of the populations will also be tabulated. In addition, the numbers of subjects who were randomized, treated, discontinued and completed will be tabulated by treatment group. Primary reasons for discontinuation of study will be tabulated.

All the protocol deviations identified prior to unblinding will be listed by subject for each treatment group.

3.2.5 *Withdrawals*

Discontinued subjects will be listed and a summary table of the number and percentage of subjects who withdrew from the study and the reasons for withdrawal will be presented by treatment group.

3.2.6 *Demographic and baseline characteristics*

Baseline value will be defined as the value measured at first visit and if missing, the last evaluable value before the first administration of study drug if any.

All demographic and baseline characteristics will be listed by treatment group and subject.

Summary statistics will be provided for demographic and baseline characteristics by treatment group, for the ITT population.

3.2.6.1 *Demographics data*

Demographic characteristics will be summarized using the following information:

- Age (years): summary statistics.
- Gender: number (%) of subjects for Male/Female.
- Country: number (%) for Algeria, Czech Republic, Egypt, Lebanon, Poland, and Tunisia.
- Body Height (cm): summary statistics.
- Body Weight (kg): summary statistics.
- BMI (kg/m^2): summary statistics and number (%) for the following categories: Underweight ($< 18.5 \text{ kg}/\text{m}^2$), Normal or Healthy Weight ($[18.5 - 25.0[\text{ kg}/\text{m}^2$), Overweight ($[25.0 - 30.0[\text{ kg}/\text{m}^2$) and Obese ($\geq 30.0 \text{ kg}/\text{m}^2$).
- Seasons of randomisation (according to date of randomisation): number (%) of subjects in each category: winter and summer.
- Virology, Bacteriology and Parasitology testing: number (%) of subjects for Positive/Negative/Not done or Missing.
- Time since diarrhoea onset: number (%) in category \leq median and $>$ median

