1.4 Known and Potential Risks and Benefits to Human Subjects

Data on the safety of diosmectite have been collected from clinical studies involving over 3000 subjects and from over 30 years of postmarketing experience. Diosmectite appears to be well tolerated and the absence of any obvious systemic treatment related side effects can be explained by the fact that systemic exposure to this medication is negligible. The most frequently described side effect of diosmectite is constipation, which is usually of mild to moderate severity and transient. However, cases of severe constipation and aggravation of pre-existing constipation have been reported very infrequently from spontaneous reporting. Hypersensitivity reactions have also been documented in subjects treated with diosmectite through spontaneous reporting. Both constipation and hypersensitivity reactions are listed events for diosmectite.

The benefits of diosmectite in the treatment of acute diarrhoea in adults have been demonstrated in a large placebo-controlled randomised clinical trial [7]. In this study, the median duration of diarrhoea was reduced by 15 hours in subjects treated with diosmectite compared with the placebo group. A reduction in the duration of diarrhoea of 15 hours (22%), allowing a more rapid return to normal activity was considered as highly clinically relevant. The amplitude of the treatment effect was comparable to that previously reported with loperamide, a reference anti-diarrhoeal medication, and direct comparative trials have not demonstrated any inferiority of diosmectite with respect to loperamide. With regard to improvement in associated symptoms, another relevant benefit in this indication, the placebo-controlled study did not demonstrate a significant treatment effect, although it was not designed or necessarily powered for this variable.

With respect to risk for the subjects, the safety profile of diosmectite is acceptable in the target indications. At last an acute diarrhoea episode in adults without concomitant alarm symptoms, according to the selection criteria, is usually self-resolving and not life-threatening. All subjects should receive recommended hydration and diet advice according to WHO guidelines [11].

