4 SELECTION AND WITHDRAWAL OF SUBJECTS

4.1 Inclusion Criteria

All subjects must fulfil all of following criteria to be included in the study:

- (1) Provision of written informed consent prior to any study related procedures,
- (2) male or female subject (outpatient) legally considered as an adult (age of majority). In Czech Republic the upper limit of age will be 70 years inclusive.
- (3) subject has a diagnosis of acute diarrhoea presumed of infectious origin, defined as:
 - the passage of 3 or more unformed loose or watery stools (rated according to the Bristol scale) per day without associated alarm symptoms*
 - having started within 48 hours before Visit 1 (first study drug intake time).
- (4) subject has, usually, normal bowel habits, (Rome III criteria) **, i.e. at least 3 stools per week and no more than 3 stools per day,
- (5) subject must be willing and able to comply with study restrictions and willing to return to the clinic for the follow up evaluation(s) as specified in the protocol.

*Symptoms considered as alarm symptoms are identified in the exclusion criteria (1)

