10.4.7 Safety Evaluation

Safety evaluation will be performed in the Safety population.

All safety data will be included in the subject data listings. Analyses and summary tables will be based upon the Safety population.

AEs will be coded according to Medical Dictionary for Regulatory Activities (MedDRA; current version at time of database lock) and will be classified by MedDRA preferred term and system organ class. AE listings will be presented by subject, system organ class and preferred term.

Incidence of all reported AEs/treatment emergent AEs (TEAEs) and SAEs will be tabulated by treatment group and overall. In addition, summary tables will be presented by maximum intensity, drug relationship and AEs/TEAEs associated with premature withdrawal of study medication.

A TEAE is defined as any AE that occurs during the active phase of the study if:

- it was not present prior to receiving the first dose of IMP, or
- it was present prior to receiving the first dose of IMP but the intensity increased during the active phase of the study, or
- it was present prior to receiving the first dose of IMP, the intensity is the same but the drug relationship became related during the active phase of the study.

Treatment emergent AEs will be flagged (*) in the AEs listings.

Concomitant medication will be coded by using WHO Drug Dictionary and will be summarised by treatment group and overall with the number and percentage of subjects receiving concomitant medication by drug class and preferred drug name.

Summary statistics (mean, median, SD and range as appropriate) by treatment group and overall will be presented for vital signs (blood pressure, heart rate in sitting position, respiratory rate, body weight at each assessment with change from Baseline).

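### AEs are collected for 7 days after treatment but count as treatment-emergent for only 48 hours, so related events with a later onset are missing from the TEAE intensity, causality and withdrawal rows

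*SAP*

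**What the plan says.** SAP 3.2.2.1 sets two windows in one paragraph. Adverse events are monitored from consent and "throughout the study until 7 days after the end of study treatment". The treatment-emergent definition then reads "A TEAE is defined as any AE that occurs during the active phase of the study", and the SAP fixes that phase as running "from the first study drug intake until 48h after last study drug intake".

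Protocol 10.4.7 has the same definition without the limit: "A TEAE is defined as any AE that occurs during the active phase of the study if", followed by the three usual conditions on events absent before dosing, worsened, or newly judged related. It does not say when the active phase ends. Both documents put the 7-day period into the safety endpoint itself (Protocol 3.2.3, SAP 3.1.3).

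In the SAP's overall summary table, the rows by intensity, by causality, by both together and for premature withdrawal are restricted to TEAEs. The AE and SAE rows are not. The tables by system organ class and preferred term cover more: "Incidence of all reported AEs, TEAEs, SAEs and non-serious AES". Further tables by maximum intensity and by drug relationship are promised, with no statement of whether they use AEs or TEAEs. SAP section 5 lists no changes from the protocol.

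**The concern.** The trial follows subjects for adverse events for a week after treatment, then leaves most of that week out of the rows a reader consults first for tolerability. An event dated to day 3 after the last sachet and judged related by the investigator is an AE but not a TEAE. It has no guaranteed place in any summary by intensity or causality.

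The expected harm makes this worth asking about. Protocol 1.4 says "The most frequently described side effect of diosmectite is constipation, which is usually of mild to moderate severity and transient", and names hypersensitivity reactions as the other listed event. Neither is confined by definition to the two days after the last dose. Clinical tolerance against placebo is a stated secondary objective.

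The cut-off also sits awkwardly beside the SAP's own missing-date rule. Under SAP 3.2.3.2, an AE with a missing or incomplete onset date is treated as a TEAE unless other data indicate otherwise, in the name of conservatism. An AE known to have started on day 3 and judged related is not a TEAE.

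**Working it through.** The plan gives no figure to reproduce here. The check compares the two windows and then traces where a late event goes.

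**Inputs**
- Collection after treatment: 7 days (SAP 3.2.2.1 and 3.1.3; Protocol 3.2.3 and 8.1).
- Treatment-emergent period after the last intake: 48 h (SAP 3.2.2.1).
- Last dosing day: Day 4 or 5, or Day 8 or 9 for a full course (Protocol 6.1). Visit 2 is on Day 5 or 6 and Visit 3 on Day 9 or 10 (Protocol 3.5).
- Not given: the AE rate, the constipation rate and the distribution of onset times.

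**Step 1: the uncovered interval.** Taking the end of treatment as the last intake, 7 × 24 = 168 h. Then 168 − 48 = 120 h, and 120/168 = 71.4%, or 5 of 7 days. This is a share of time, not of events.

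**Step 2: where an event dated >48 h to 168 h after the last sachet appears**

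| SAP output | Late event |
|---|---|
| Overall summary, AE row (and SAE row if serious) | counted |
| Overall summary, TEAE rows: any, intensity, causality, both, withdrawal | not counted |
| Class/term tables of all AEs, non-serious AEs, SAEs, by arm | counted in those that apply |
| Class/term table of TEAEs | not counted |
| Maximum-intensity and drug-relationship tables | basis not stated |
| Withdrawal table (TEAEs/SAEs) | only if serious |
| Listings | present without the TEAE flag, with time since last intake (SAP 3.2.12) |

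**Step 3: what share of post-dose onsets could this be?** The documents do not say, so this is a range under assumed timing. For uniform onset over 168 h the share is 120/168 = 71%. For exponential onset with median m hours, truncated at 168 h, the share is (2^(−48/m) − 2^(−168/m)) / (1 − 2^(−168/m)). For m = 24 this is (0.2500 − 0.0078)/(1 − 0.0078) = 24%.

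| Assumed median onset after last sachet | Share later than 48 h |
|---|---|
| 12 h | 6% |
| 24 h | 24% |
| 36 h | 37% |
| 48 h | 45% |
| 72 h | 54% |

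The range is wide, and it applies only to events that start after dosing has ended, whose number is unknown.

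**Step 4: would late events be captured at all?** From the last dosing day to the visit that follows is 5 − 5 = 0 to 6 − 4 = 2 days for Visit 2, and 9 − 9 = 0 to 10 − 8 = 2 days for Visit 3 after a full course. A subject who recovers and stops between the visits has a longer interval: stopping on Day 6 leaves 9 − 6 = 3 or 10 − 6 = 4 days to Visit 3. Otherwise an event in the uncovered interval reaches the database only if reported after the last visit. Protocol 5.2.3 and 5.2.4 ask for this collection but schedule no contact for it.

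**The case against.** The strongest reply is that a treatment-emergent window shorter than the collection window is a common and legitimate choice. The protocol leaves the end of the active phase open, and Protocol 10.4 hands the rules for derived variables to the SAP. Filling in an undefined term is the SAP's job. That stands. A reader might infer that the SAP contradicts the protocol, or that its empty list of changes is false; the documents show neither. What remains is that the choice is unexplained.

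Late events also stay visible. They are in the all-AE and non-serious AE or SAE tables by arm, and the listings show time since last intake. Consent and first dose both fall at Visit 1, so few pre-dose events dilute the all-AE table. This stands too. The gap is confined to TEAE-based output, and in particular to the intensity, causality and withdrawal rows.

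Three stronger readings are tempting and are not supported.

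- **That all constipation appearing after dosing is dropped.** Onset within 48 h of the last sachet is still treatment-emergent, and incomplete onset dates default to TEAE.
- **That constipation cannot be recognised within 48 h.** The eligibility criterion for normal habit is "at least 3 stools per week and no more than 3 stools per day". Three stools a week give a mean gap of 168/3 = 56 h, but this is the lower end of the range; three a day give 24/3 = 8 h. More importantly, the TEAE rule turns on when an event occurs, not when it is noticed. Constipation recognised on day 3 may carry an earlier onset date, and hard stools (Bristol types 1 and 2) can reveal it without any change in frequency.
- **That the cut-off favours the active arm.** This needs more late events on diosmectite than on placebo beyond 48 h, and the documents give no rate for either arm.

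The withdrawal row matters least. For a subject dosed to schedule, participation has usually ended before an event beyond 48 h could cause withdrawal.

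**Conclusion.** The point holds in a limited form. AEs with a dated onset more than 48 h and up to 7 days after the last sachet are collected but excluded from every TEAE summary, so those judged related or severe do not reach the intensity and causality rows of the overall table. The interval is 120 of 168 h. Whether the separate maximum-intensity and drug-relationship tables recover these events cannot be told, because their basis is not stated.

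The number of events affected and any imbalance between arms cannot be derived. The number may be small, given how soon after dosing the last visit mostly falls. The conclusion assumes that onset dates are recorded and that the end of treatment means the last intake. The issue concerns descriptive safety output only; the confirmatory analysis of time to recovery is untouched. It is a cheap improvement to the SAP, not a flaw that threatens the trial's conclusions.

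**What to change.** In SAP 3.2.2.1:

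1. Define the treatment-emergent window as first intake to 7 days after last intake, so that it matches the collection window.
2. Show TEAEs split by onset up to 48 h versus more than 48 h after the last intake. This keeps the sponsor's present view.
3. State that the maximum-intensity and drug-relationship tables use this TEAE definition.
4. State how the 48 h split is computed. The diary records sachets per day (Protocol 5.2.5 and 7.4), and SAP 3.2.8 mentions a time of intake only for on-site dosing, so a date-based rule is likely to be needed.

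The cost is one phrase, one programming constant and one extra split, with no new data collection. The downside is that a few unrelated late events in both arms will be counted as TEAEs; the split shows how many.

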For all AEs, the investigator must pursue and obtain information adequate both to determine the outcome of the AE and to assess whether it meets the criteria for classification as a SAE requiring immediate notification to the sponsor or its designated representative. For all AEs, sufficient information should be obtained by the investigator to determine the causality of the AE (i.e. IMP or other illness). The investigator is required to assess causality and record that assessment on the CRF/eCRF. Follow up of the AE, after the date of IMP discontinuation, is required if the AE or its sequelae persist. Follow up is required until the event or its sequelae resolve or stabilise at a level acceptable to the investigator and the sponsor’s clinical monitor or his/her designated representative.

8.1.4 *Reporting of Serious Adverse Events*

All SAEs (as defined below) regardless of treatment group or suspected relationship to IMP must be reported immediately (within 24 hours of the investigator’s knowledge of the event) to the pharmacovigilance contact specified at the beginning of this protocol. If the immediate report is submitted by telephone, this must be followed by detailed written reports using the SAE report form.

A SAE is any AE that:

- (1) Results in death.
- (2) Is life-threatening, that is any event that places the subject at immediate risk of death from the event as it occurred. It does not include an event that, had it occurred in a more severe form, might have caused death.
- (3) Results in inpatient hospitalisation or prolongation of existing hospitalisation, excluding admission for social or administrative reasons (see further).
- (4) Results in a persistent or significant disability/incapacity, where disability is a substantial disruption of a person’s ability to conduct normal life functions.
- (5) Results in congenital anomaly/birth defect in the offspring of a subject who received the IMP.
- (6) Is an important medical event that may not result in death, be life threatening, or require hospitalisation when, based upon appropriate medical judgement, may jeopardise the subject and may require medical or surgical intervention to prevent one of the outcomes listed in this definition. Examples of such medical events include allergic bronchospasm requiring intensive treatment in an emergency room or at home, blood dyscrasias or convulsions that do not result in in-patient hospitalisation, or the development of drug dependency or drug abuse.

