10.4.3 Subject Disposition and Withdrawals

The numbers and percentages of subjects enrolled and included in populations will be tabulated by country. The reasons for subject exclusions from each of the populations will also be tabulated. In addition, the numbers of subjects who were randomised, discontinued and completed will be tabulated by treatment group. Primary reasons for discontinuation of study treatment will be tabulated.

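### The SAP tabulates adverse events leading to withdrawal from the study where the protocol specifies withdrawal of study medication, and it does not declare the change

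*SAP*

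**What the plan says.** On adverse events, protocol 10.4.7 and the synopsis plan summary tables of "AEs/TEAEs associated with premature withdrawal of study medication". In SAP 3.2.2.1 the overall summary table has a row for "TEAE leading to premature withdrawal of study", and a further summary table covers "TEAEs/SAEs associated with premature withdrawal of study". The same section announces a listing of "adverse events leading to withdrawal and listings of deaths will also be presented", without saying what is withdrawn from.

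On disposition, protocol 10.4.3 states: "Primary reasons for discontinuation of study treatment will be tabulated". SAP 3.2.4 states: "Primary reasons for discontinuation of study will be tabulated".

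SAP section 5, which is reserved for changes from the protocol, is marked as not applicable.

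**The concern.** Stopping the medication and leaving the study are different events in principle. If they come apart in practice, the SAP's tables answer a narrower question than the protocol's. They count people who left, not people who could not or would not continue the sachets because of an adverse event. Clinical tolerance versus placebo is a secondary objective (protocol 2.2), and the share of subjects who stop a drug because of an adverse event is a standard measure of it.

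The same substitution occurs in two separate parts of the SAP and is not declared. A reader of the study report would therefore assume that the protocol's tables had been delivered.

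**Working it through.** No figure in the plan is at stake, so the check is a comparison of texts followed by a trace of one subject.

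**Step 1: the texts side by side.**

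| Output | Protocol | SAP |
|---|---|---|
| Withdrawal row, overall AE table | No such row named | 3.2.2.1: leaving the study |
| AE-withdrawal summary table | 10.4.7 and synopsis: stopping medication | 3.2.2.1: leaving the study |
| Reasons for discontinuation | 10.4.3: stopping treatment | 3.2.4: leaving the study |
| Listing of AEs leading to withdrawal | No such listing named | 3.2.2.1: kind not stated |
| Declared changes | n/a | Section 5: none |

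SAP 3.2.5 separately tabulates the reasons subjects withdrew from the study. As worded, SAP 3.2.4 therefore largely repeats 3.2.5, and no disposition table covers stopping treatment.

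**Step 2: are the two terms interchangeable here?** SAP 1.3.2.4 explains discontinuation from the study as giving up participation before the protocol is complete. The protocol also mentions stopping the investigational product as an event in its own right:

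- 8.1.2.6: abnormal findings that lead to it.
- 8.1.3: "Follow up of the AE, after the date of IMP discontinuation, is required if the AE or its sequelae persist".
- 8.1.5: in pregnancy.
- 8.1.7: because of a serious adverse event.

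On the other side, 6.3 and 8.1.7 write IMP discontinuation and study withdrawal as a pair. No section says whether a subject who stops sachets for an adverse event stays in the study. The terms are thus distinct in wording, but the documents do not settle whether they separate in practice.

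**Step 3: which stops are premature?** Under protocol 6.1, 24 sachets are mandatory, after which treatment stops on recovery or at 48 sachets. Stopping on recovery after the mandatory sachets is the planned course and does not count. What remains is stopping before 24 sachets, or stopping later without recovery and short of the maximum. There is room for the first kind. At six sachets a day the mandatory course takes 24 / 6 = 4 days, while the planning medians for recovery are 55 and 70 hours (protocol 10.2), both below 3 × 24 = 72 hours. This shows opportunity only; it gives no rate.

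**Step 4: trace one subject** who stops sachets prematurely because of a treatment-emergent event and then attends the remaining visits.

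| SAP output | Counted? |
|---|---|
| Safety population (2.2) | Yes |
| AE, TEAE, intensity and causality rows, and SAE row if serious (3.2.2.1) | Yes |
| Incidence by system organ class and preferred term; full AE listing | Yes |
| Overall-table row for study withdrawal | No |
| Summary table for study withdrawal | No |
| Reasons for discontinuation of study (3.2.4) | No |
| Listing of AEs leading to withdrawal | Undetermined |

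Under the protocol's wording this subject would be counted both as an adverse event withdrawal and in the reasons for discontinuation.

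**The case against.** The strongest reply is that the two definitions may select the same people. Protocol 6.3 joins the two kinds of stopping with a slash and refers to 4.3 for the criteria, yet 4.3 describes only withdrawal from the study. Section 8.1.7 pairs the terms as well, and 5.2.4 treats adverse event withdrawal under study discontinuation. If sites handle every adverse-event stop as a study withdrawal, nothing is lost. This stands as a limit on size: the effect may be zero. It does not make the SAP's wording equivalent to the protocol's.

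Second, early stopping is partly visible elsewhere. SAP 3.2.8 summarises sachets taken in the mandatory period, drug exposure and a compliance class below 80%. That is correct, but none of these outputs links stopping to an adverse event.

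Third, the table shells are not visible in the public SAP and may define the withdrawal table more precisely, and the listing may be broad enough to include these subjects. Both are possible. The SAP text should still carry the definition.

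Fourth, the safety summaries are descriptive and only the primary analysis is confirmatory (SAP 3.1.4). This limits the consequence to the tolerability description.

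A reader might also infer two stronger claims. One is that such subjects vanish from the main adverse event table; the trace shows that they do not. The other is that adverse-event stopping is understated mainly in the active arm, because constipation is the side effect most often described. Protocol 1.4 calls it usually mild to moderate and transient, which fits continuing as well as stopping, and the documents give no rate for either arm.

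**Conclusion.** The discrepancy is real. It occurs in the overall-table row, the summary table and the disposition table, and the SAP does not declare it. Its effect is confined to those three outputs. Each omits a subject who stops medication prematurely for a treatment-emergent event but completes the study visits, while every other applicable safety output keeps that subject.

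The number affected cannot be derived from the documents, zero is possible, and no direction by arm can be claimed. The conclusion rests on one assumption: that at least some subjects can stop sachets for an adverse event without being withdrawn from the study, which the protocol neither states nor rules out. The primary analysis is untouched. The change is worth making because tolerability is a stated objective and following the protocol's own definition costs almost nothing.

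**What to change.** - **SAP 3.2.2.1:** add TEAEs leading to premature discontinuation of study medication, both as a row in the overall table and as a table by system organ class and preferred term, with study withdrawal shown beside it. State that stopping on recovery after the mandatory sachets is not premature. Say whether the listing of adverse events leading to withdrawal refers to medication, study or both.
- **SAP 3.2.4:** tabulate the primary reasons for discontinuing study treatment as well as those for discontinuing the study.

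The cost is a few table rows and some wording. The one real task comes before unblinding: the team must confirm which collected field holds the reason for stopping sachets. The documents describe recording the reason for study discontinuation (protocol 5.2.4, SAP 1.3.2.4) and the daily sachet count in the diary, but they show no field for the reason sachets alone were stopped.
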